14 GOOD CLINICAL PRACTICES (“GCP”)

14.1 Institutional Review Board (IRB) Approval

Prior to study initiation, this protocol, the informed consent and any advertisements for subject recruitment must be submitted to the IRB for written approval. The IRB’s written notification of approval will be provided to the MD Anderson IND Office prior to study commencement. Any changes to the protocol that may increase study risks or present new risks to the subject or may adversely affect the outcome of the study must be approved in writing by the MD Anderson IND Office and the site IRB before the change is made.

14.2 Informed Consent

Subjects must provide informed consent in writing after having adequate time to consider their participation in the study pursuant to the Declaration of Helsinki requirements and local / US regulations. Consent must be obtained prior to any protocol-related procedures that are not part of the subject’s standard care. Written documentation of consent must be provided on the signature page in addition to a note in the study records indicating the date that consent was obtained. The subject or his/her legal representative should receive a signed copy of the consent form according to international GCP guidelines.

14.3 Subject Confidentiality

All information concerning subjects or their participation in this trial will be considered confidential. Only authorized personnel and designated consultants will have access to these confidential files. Authorized regulatory personnel have the right to inspect and copy all records pertinent to this trial. Enrolled subjects will be assigned a unique identifier that will be used to maintain confidentiality of subjects’ medical information. Subject names and other protected health information will not be captured on the case report forms.

14.4 Data Collection

The Case Report Form (CRF) is the primary data collection instrument for the study. REDCap™ will be used as the electronic case report form. Primary data collection based on source documented hospital chart reviews will be performed clearly and accurately by the site personnel on the CRF. All missing data will be explained. If the item is not

applicable to the individual case, “N/A” will be written in the field. All entries will be printed legibly in black ink. To correct an error that has been made, a single line will be drawn straight across the incorrect entry and the correct data will be entered above it. All changes will be initialed and dated. A copy of the completed Case Report Forms will remain on site at the participating institution.

Study data will be collected and managed using REDCap (Research Electronic Data Capture) electronic data capture tools hosted at MD Anderson. [ref] REDCap (www.project-redcap.org) is a secure, web-based application with controlled access designed to support data capture for research studies, providing: 1) an intuitive interface for validated data entry; 2) audit trails for tracking data manipulation and export procedures; 3) automated export procedures for seamless downloads to common statistical packages; and 4) procedures for importing data from external sources. In the case of multi-center studies REDCap uses Data Access Groups (DAGs) to ensure that personnel at each institution are blinded to the data from other institutions. REDCap (<https://redcap.mdanderson.org>) is hosted on a secure server by MD Anderson Cancer Center's Department of Research Information Systems & Technology Services. REDCap has undergone a Governance Risk & Compliance Assessment (05/14/14) by MD Anderson's Information Security Office and found to be compliant with HIPAA, Texas Administrative Codes 202-203, University of Texas Policy 165, federal regulations outlined in 21CFR Part 11, and UTMDACC Institutional Policy #ADM0335. Those having access to the data file include the study PI and research team personnel. All protected health information (PHI) will be removed from the data when it is exported from REDCap for analysis. All dates for a given patient will be shifted by a randomly generated number between 0 and 364, thus preserving the distance between dates. Dates for each patient will be shifted by a different randomly generated number. Following publication study data will be archived in REDCap.

14.5 Data Monitoring and Quality Control

All collected data will be verified for accuracy with source documents including, but not limited to, medical records, office/clinic notes, procedure reports, laboratory results, physician and nursing progress notes. Verification and quality of data, monitoring of clinical study progress and Investigator compliance with the approved protocol will be conducted by the MD Anderson IND Office or a designated representative.

The MD Anderson IND Office or its designated representative will be allowed to visit the clinical site and have direct access to all study records throughout the duration of the study. The monitor will review all source data and compare them to the data documented in the case report forms, in addition to performing a review of the Regulatory Binder, and conducting device accountability. The Investigator and/or institution will provide direct

access to source data/documents for trial-related monitoring, audits, IRB review and regulatory inspection.

14.6 Record Retention

The Study Sponsor and Investigator will retain essential documents relating to this clinical study for at least two (2) years after study completion or two (2) years post marketing approval, whichever is longer. Records may be retained for a longer period as agreed to by the Study Sponsor and Investigator.

14.7 Protocol Monitoring Plan

This is a single-arm study and, therefore, does not require MD Anderson's Data Safety Monitoring Board (DSMB) review. This study will be monitored by the MD Anderson IND Office and the Principal Investigator. A protocol-specific monitoring plan will be followed.

The trial will be stopped if flap failures are observed in 2 of the first 5 patients treated. The trial will also be stopped if flap failures are observed in 2 of the second set of 5 patients treated. Flap failure is defined as irreversible arterial and venous thrombosis detected by implantable or surface doppler signal within 72 hours after surgery. Notice will be provided to the Principal Investigator, the IRB, and the FDA should early termination of the trial be recommended. The trial will not restart until a thorough risk analysis has been completed and the FDA and IRB provide their written approval to restart the study.

15 Protocol Deviations

[name] and [name] will not deviate from the protocol except in medical emergencies. If a medical emergency occurs, prior approval will not be required but the IRB must be notified of the deviation in accordance with Chapter 25, Reporting Requirements and Timeframes of MD Anderson's IRB Policy on Reporting Protocol Deviations.

16 Device Accountability

The *da Vinci*® robotic surgical system and the corresponding instruments that will be used in this study have been FDA cleared for a variety of surgical indications. [name] and [name] will use the *da Vinci*® robotic surgical system and instruments that are currently in use at MD Anderson for other cleared clinical indications. MD Anderson will ensure that the Investigator and clinical site personnel are aware they must report any device malfunction related to this study to Intuitive Surgical within 24 hours. In addition, clinical site personnel must complete the Device Performance Issue-Malfunction case report form (Appendix H).

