12 STATISTICAL ANALYSIS PLAN

This is a prospective, non-randomized, single-arm study designed to assess the safety and feasibility of the *da Vinci*® robotic surgical system in latissimus dorsi muscle flap harvest procedures. A maximum of 15 subjects requiring latissimus dorsi flap harvest procedures in conjunction with breast, scalp, upper extremity, or lower extremity reconstruction procedures will be enrolled at MD Anderson in Houston, Texas.

The muscle flap failure will be monitored using the Bayesian stopping boundaries calculated based on beta-binomial distribution. We will consider that the *da Vinci*® robotic surgical system is promising in latissimus dorsi flap harvest if the muscle flap failure rate is below 10%. With a sample size of 15 patients, the probability of observing at least one muscle flap failure is 79.4%. The prior probability of muscle flap failure is modeled by beta distribution (Beta (0.1, 0.9)). Denoting the probability of muscle flap failure by θ , and it is compared to fixed target of 10%. The following decision criterion will be applied: Stop if $\text{Prob}\{\theta > 0.10 \mid \text{data}\} > 0.75$.

Patients will be monitored by a cohort size of 5 according to the following stopping boundaries for muscle flap failure. The patient enrollment will be halted for this safety monitoring because the status of muscle flap failure can be obtained right after surgery.

Number of patients evaluated	Stop if \geq muscle flap failure observed
5	2-5
10	2-10
15	Always stop with this many patients

The operating characteristics are summarized in the following table (based on simulations from 10,000 trials).

True DLT Rate	Prob (stop the trial early)
0	0
0.05	0.0861
0.10	0.2639
0.15	0.4557
0.20	0.6242
0.25	0.7560
0.30	0.8507

The above stopping boundaries and operating characteristics are calculated using MultcLean (v.2.1.0) design software downloaded from <http://biostatistics.mdanderson.org/SoftwareDownload>.

The muscle flap failure rate and its 95% confidence interval (CI) will be calculated using the exact method. Other outcome data to be collected will include: pain assessment using a validated VAS, QuickDASH score, and physical therapy assessment.

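### Section 14.7 restates the flap-failure stopping rule per set of five patients and leaves out one outcome, one failure in each of the first two sets, for which Section 12 stops

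*Combined protocol and SAP*

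**What the plan says.** **Section 12 (Statistical Analysis Plan).** Flap failure is monitored with a beta-binomial rule: prior Beta(0.1, 0.9), fixed target 10%. "The following decision criterion will be applied: Stop if" the posterior probability that the failure rate exceeds 0.10 is above 0.75. Looks come every five patients: "Patients will be monitored by a cohort size of 5 according to the following stopping boundaries for muscle flap failure". The boundary table is indexed by the number of patients evaluated and stops with 2 to 5 failures at 5 patients and 2 to 10 failures at 10 patients; 15 patients is the end of the trial. Accrual pauses for each look: "The patient enrollment will be halted for this safety monitoring". The probabilities of stopping early are then tabulated for true rates from 0 to 0.30.

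**Section 14.7 (Protocol Monitoring Plan).** The rule is restated without reference to Section 12. The first trigger is: "The trial will be stopped if flap failures are observed in 2 of the first 5 patients treated". The second is: "The trial will also be stopped if flap failures are observed in 2 of the second set of 5 patients treated". The section also says: "A protocol-specific monitoring plan will be followed". That plan is not among the documents supplied.

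**The concern.** The upper limit of 10 failures in the 10-patient row of Section 12 is possible only if the count runs over all ten patients, so the second look is cumulative. The second trigger in Section 14.7 counts failures only within patients 6 to 10. The two forms must therefore differ when failures are split between the sets.

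The point matters because Section 14.7 reads as a complete operational rule. It names who monitors the trial, defines flap failure with a time window, and sets out the notification and restart steps. It also says that DSMB review is not required, so the written rule carries the weight. Someone working from that section alone finds no instruction to stop after one failure in each set, and the trial could run on to 15 patients with the Section 12 criterion already met.

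**Working it through.** **Inputs.** From Section 12: prior Beta(0.1, 0.9), target 0.10, cutoff 0.75, looks at 5 and 10, maximum 15, and the published table. From Section 14.7: the two per-set triggers, with 2 read as 2 or more. Let *a* and *b* be the failures in patients 1–5 and 6–10, independent and binomial(5, *p*).

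**Step 1: the Section 12 boundary.** With *x* failures in *n* patients the posterior is Beta(0.1 + *x*, 0.9 + *n* − *x*). The probability that the rate exceeds 0.10 is:

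| Data | Posterior | Probability | Section 12 action |
|---|---|---|---|
| 1/5 | Beta(1.1, 4.9) | 0.6409 | continue |
| 2/5 | Beta(2.1, 3.9) | 0.9331 | stop |
| 1/10 | Beta(1.1, 9.9) | 0.3926 | continue |
| 2/10 | Beta(2.1, 8.9) | 0.7646 | stop |

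The boundary table follows from its stated inputs.

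**Step 2: the published stopping probabilities.** Under the cumulative rule the trial stops early if *a* ≥ 2 or *a* + *b* ≥ 2. The first condition implies the second, so

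P(stop) = 1 − (1−*p*)^10 − 10*p*(1−*p*)^9.

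At *p* = 0.10 this is 1 − 0.3487 − 0.3874 = 0.2639, as published. All six non-zero entries agree to four decimals.

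**Step 3: Section 14.7 alone.** The trial stops early if *a* ≥ 2 or *b* ≥ 2. With *q* = 1 − (1−*p*)^5 − 5*p*(1−*p*)^4,

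P(stop) = 1 − (1−*q*)^2.

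At *p* = 0.20, *q* = 0.2627 and P(stop) = 1 − 0.7373² = 0.4564.

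**Step 4: where the rules part.** Of the 36 pairs (*a*, *b*), only (1, 1) is treated differently. Every Section 14.7 trigger is also a Section 12 trigger. The gap is therefore

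P(1, 1) = [5*p*(1−*p*)^4]²,

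which at *p* = 0.20 is 0.4096² = 0.1678.

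| True rate | Section 12 (published and reproduced) | Section 14.7 alone | Gap |
|---|---|---|---|
| 0.05 | 0.0861 | 0.0447 | 0.0415 |
| 0.10 | 0.2639 | 0.1563 | 0.1076 |
| 0.15 | 0.4557 | 0.3024 | 0.1533 |
| 0.20 | 0.6242 | 0.4564 | 0.1678 |
| 0.25 | 0.7560 | 0.5995 | 0.1564 |
| 0.30 | 0.8507 | 0.7210 | 0.1297 |

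(Gaps are computed before rounding.)

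**Step 5: which look is affected.** First-look stops are the same under both (0.1648, 0.2627, 0.3672, 0.4718 at 15% to 30%). The whole gap falls at 10 patients: 0.2909, 0.3615, 0.3888, 0.3789 under Section 12 against 0.1376, 0.1937, 0.2324, 0.2492 under Section 14.7 alone.

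**Step 6: how usual the split is.** A trial that reaches the second look with exactly 2/10 has either (0, 2), with 10 placements, or (1, 1), with 5 × 5 = 25. So 25/35 = 71% of such trials have one failure in each set, whatever the true rate.

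**Step 7: patients treated.** Keeping looks at 5 and 10 for both rules, each missed stop adds 5 patients, so the mean excess is 5 × gap: 0.77, 0.84, 0.78 and 0.65 patients per trial at 15% to 30%. The means are 11.90, 10.57, 9.38, 8.39 under Section 12 and 12.66, 11.40, 10.17, 9.04 under Section 14.7 alone.

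**The case against.** The strongest reply is that the two sections belong to one protocol and can be obeyed together. Section 12 is mandatory. Section 14.7 nowhere says that its triggers are the only ones or that the trial continues otherwise. Applied jointly, they give exactly the published table. On that view Section 14.7 is an incomplete restatement, and the shortfall describes only a reader who skips Section 12. All of this is true, and it limits the finding: Section 12 is sound and joint application loses nothing. But the protocol does not tell the reader to combine the sections or which governs, and Section 14.7 does not point back to Section 12.

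A second reply is that Section 14.7 sets no looks. If it stops at the second failure within a set, its mean number of patients is 12.31, 10.84, 9.38 and 8.04 at 15% to 30%, and the excess over Section 12 shrinks, vanishes at 25% and reverses at 30%. That comparison mixes immediate stopping under one rule with look-based stopping under the other. With immediate stopping under both, the excess is about 1.2 to 1.4 patients. The figures in Step 7 do borrow the Section 12 looks and should be read on that condition. The stopping probabilities do not depend on it.

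Third, 2/10 only just crosses the cutoff (0.7646 against 0.75), the trial is a small pilot, and the separate monitoring plan may settle matters. The margin is narrow, but Section 12 lists 2/10 explicitly as a stop. What the monitoring plan says is unknown, and it would not remove the discrepancy from the protocol itself.

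**Conclusion.** The concern holds and must be fixed. The protocol states the stopping rule for its primary safety endpoint in two non-equivalent forms, and the published operating characteristics fit only the cumulative one. In terms of failure counts, the forms differ at exactly one outcome: one failure in each of the first two sets.

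If Section 14.7 is followed alone, the probability of stopping early is 13 to 17 percentage points below the published value at true rates of 15% to 30%, and 0.1563 against 0.2639 at the 10% target itself. At 5% it is 0.0447 against 0.0861, but a missed stop there is a false alarm avoided under the protocol's own target and is not counted as a safety loss. At most 5 further patients would be treated in any one trial.

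The figures assume independent failures at a constant rate, 2 read as 2 or more in Section 14.7, and, for patients treated only, looks after 5 and 10. How the rule is applied in practice cannot be judged without the monitoring plan.

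**What to change.** Reconcile the two passages so that one rule stands in both, with the operating characteristics of that rule. The choice is the sponsor's.

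- **If the cumulative count is intended:** reword the second trigger in Section 14.7 as 2 or more failures among the first 10 patients, and the first as 2 or more among the first 5. Section 12 stays as it is. Cost: about one sentence.
- **If the per-set count is intended:** Section 12 must say that the criterion is applied to each set of five separately, so that the first five patients are left out of the calculation at the second look. Its 10-patient row becomes 2 or more among patients 6–10, and its table becomes 0, 0.0447, 0.1563, 0.3024, 0.4564, 0.5995, 0.7210 for true rates 0 to 0.30. The prior and cutoff can remain, since 1/5 gives 0.6409 (continue) and 2/5 gives 0.9331 (stop). The text should acknowledge that the trial would then continue at one failure in each set, where the criterion on all ten patients gives 0.7646. Cost: one or two sentences, one boundary row and the table.

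In either case Section 14.7 should refer to Section 12, and the separate monitoring plan should be checked against the agreed wording. Neither option needs extra patients or procedures.

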17 SPONSOR RESPONSIBILITIES

As the [name] Anderson is committed to the following activities pursuant to international GCP guidelines:

- 1) Securing the necessary IRB and government approvals for this protocol;
- 2) Obtaining all required approvals prior to device usage under this investigational protocol;
- 3) Selecting a qualified investigator;
- 4) Ensuring proper investigator training;
- 5) Ensuring proper clinical site monitoring;
- 6) Ensuring that the IRB is informed of any significant new information about the study;
- 7) Maintaining accurate and complete study records and submitting required reports;
- 8) Obtaining a signed clinical trial / investigator agreement;
- 9) Providing case report forms and ensuring that the completed forms match source documentation;
- 10) Ensuring protocol compliance; and
- 11) Ensuring proper reporting of all AEs.

18 INVESTIGATOR RESPONSIBILITIES

[name] will sign a Clinical Trial Agreement affirming that he will adhere to the following activities pursuant to international GCP guidelines:

- 1) Ensuring that enrolled subjects comply with the inclusion/exclusion criteria;
- 2) Obtaining written IRB approval prior to study initiation;
- 3) Obtaining written informed consent from each subject prior to enrollment;
- 4) Performing the study evaluations as described in this protocol;
- 5) Maintaining source documentation in the subject's medical files;
- 6) Completing case report forms corroborated by source documentation;
- 7) Submitting required reports to the Study Sponsor, IRB and regulatory authorities;
- 8) Complying with the study protocol and reporting any deviations in advance of their occurrence;
- 9) Maintaining study related records;
- 10) Maintaining accurate records related to device accountability; and
- 11) Ensuring proper reporting of all AEs.

19 STUDY MONITORING

The study monitor is a Clinical Research Monitor employed by the IND/IDE sponsor (MD Anderson). The Clinical Research Monitor will monitor the clinical study and report the

findings directly to the Medical Monitor and Vice President of Clinical Research. There will be one Clinical Research Monitor monitoring the study.

20 COMPENSATION IN THE EVENT OF INJURY

If the subject suffers injury as a direct result of taking part in this study, MD Anderson health providers will provide medical care. However, this medical care will be billed to the subject's insurance provider or the subject in the ordinary manner. The subject will not be reimbursed for expenses or compensated financially by MD Anderson for this injury.

The subject may also contact the Chair of MD Anderson's IRB at [contact] with questions about study-related injuries. By signing the consent form, the subjects are not giving up any of their legal rights.

Certain tests, procedures, and/or drugs that the subject may receive as part of this study may be without cost to the subject because they are for research purposes only. However, the subject's insurance provider and/or the subject may be financially responsible for the cost of care and treatment of any complications resulting from the research tests, procedures, and/or drugs, including hospitalization, nausea, vomiting, low blood cell counts, and dehydration. Standard medical care that the subjects receive under this research study will be billed to the subject's insurance provider and/or the subject in the ordinary manner. Before taking part in this study, the subject may ask about which parts of the research-related care may be provided without charge, which costs the subject's insurance provider may pay for, and which costs may be the subject's responsibility. The subject may ask that a financial counselor be made available to the subject to talk about the costs of this study.

There are no plans to compensate the subject for any patents or discoveries that may result from the subject's participation in this research.

The subject will receive no compensation for taking part in this study.

